7.3 VARIABLES

Variables related to the study period will be defined as follows:

Aim 1

- **Fibrosing ILD diagnosis date**—The first ILD diagnosis date for patients with ≥ 2 fibrosing ILD diagnoses on different dates and within 365 days. The fibrosing ILD diagnosis date is the first day of follow-up observation time for Aim 1.
- **Pre-ILD baseline period**—The 12-month period prior to the fibrosing ILD diagnosis date.
- **Aim 1 follow-up period**—The variable period starting on the fibrosing ILD diagnosis date and continuing until the earliest of the following: disenrollment from the health plan, death, or end of the study period. The Aim 1 follow-up period will be used to assess Aim 1 outcomes.
 - **All-cause mortality**—Death will be used as a censoring event and is further defined in Section 7.3.3.1.

Aim 2

- **Index date**—For the oxygen therapy cohort, the first date following the fibrosing ILD diagnosis date with a claim with diagnosis for oxygen therapy; for the no oxygen therapy cohort, a date within the same continuous enrollment period as the fibrosing ILD diagnosis date that is similar to the matched oxygen therapy patient in time from fibrosing ILD to index date. The index date is the first day of follow-up observation time for Aim 2 and Further Aim.
- **Pre-index baseline period**—The 12-month period prior to the index date.
- **Aim 2 follow-up period**—The variable period starting on the index date until the earliest of the following: disenrollment from the health plan, death, or the end of the study period. Matched pairs will be given the same duration of follow-up. The Aim 2 follow-up period will be used to assess Aim 2 and Further Aim outcomes.
 - **All-cause mortality**—Death will be used as a censoring event and is further defined in Section 7.3.3.1.

An overview of the analytic study variables and the study periods for which each analytic variable will be reported is provided in Table 1. Additional variable information is provided in Sections 7.3.1 to 7.3.4.

Table 1. Analytic Variables by Data Source and Time Period

Characteristic	Data source		Aim 1 time period		Aim 2 time period	
	Claims*	EHR	Pre-ILD baseline	Follow-up	Pre-index baseline	Follow-up
Aim 1 outcomes						
Oxygen therapy (time to initiation, sustained oxygen therapy use)		X		X	X	
Aim 2 outcomes						
Disease progression	X	X				X
All-cause mortality	X					X
Hypoxemia	X	X	X		X	X
Acute exacerbations	X	X				X
Patient characteristics†						
Index year	X		X		X	
Age/age groups	X		X		X	
Race/ethnicity	X		X		X	
Sex	X		X		X	
Insurance type	X		X		X	
Geographic region	X		X		X	
Clinical characteristics						
Underlying ILD type‡	X		X		X	
Respiratory diseases	X		X		X	
Smoking	X		X		X	
Quan-Charlson comorbidity score	X		X		X	
AHRQ comorbid conditions	X		X		X	
Smoking	X		X		X	
Pulmonary rehabilitation	X		X		X	
Healthcare utilization characteristics						
Provider specialty	X		X		X	
Medication use	X		X		X	
All-cause HCRU and costs	X		X		X	

*As available among the subset of patients with information from both EHR and claims

†Measured as of the index date, or first available claim after the index date with value values for each of the characteristics

‡Measured using claims from the entire study period

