5. RATIONALE AND BACKGROUND

Interstitial lung disease (ILD) is a broad term that describes more than 200 diverse lung disorders, including idiopathic pulmonary fibrosis (IPF), autoimmune ILD, hypersensitivity pneumonitis (HP), and sarcoidosis.¹ Typical symptoms of ILD include cough and dyspnea, as well as decreased lung capacity², which leads to exercise intolerance and hypoxemia.

The major goal of therapy in ILD patients is to slow disease progression as well as improve the associated dyspnea, exercise capacity, and health-related quality of life.³ Approved treatment options for fibrosing ILD comprise antifibrotic treatments including nintedanib and pirfenidone, which slow the rate of decline in forced vital capacity (FVC). Other commonly prescribed treatment options are corticosteroids, immunosuppressants, opioids, and lung transplantation.⁴ Despite advances in pharmacotherapy, many patients continue with disease progression. Oxygen therapy is commonly administered to reduce breathlessness and increase physical capacity by improving gas exchange.⁵

Supplemental oxygen (O₂) is commonly prescribed in clinical practice for patients with fibrotic ILD; however, robust evidence to support its long-term use is lacking. Recommendations for long-term oxygen therapy (LTOT) for resting hypoxemia in ILD are largely extrapolated from trials conducted in chronic obstructive pulmonary disease (COPD), where a survival benefit is well established.^{6,7} The American Association for Respiratory Care guideline recommends the use of oxygen therapy to maintain the oxygen saturation (SpO₂) range of 94–98% for most hospitalized patients.⁸ Despite its frequent use, there is a paucity of studies evaluating the incidence, prevalence, and impact of LTOT on outcomes such as disease progression or mortality in ILD. This study will help fill in the gaps in increasing the understanding of the use of oxygen therapy among fibrosing ILD patients and assess whether the use of oxygen leads to better or worse outcomes.

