7.2 SETTING

7.2.1 Secondary data source selection

The study will use administrative claims and EHR data from Optum's Market Clarity Integrated Claims + Clinical database.

7.2.2 Study population: Aim 1

The analysis for Aim 1 will include patients newly diagnosed with fibrosing ILD during the patient identification period. Patients must meet the following selection criteria to be included in the study:

Inclusion Criteria

- ≥ 2 fibrosing ILD diagnoses in any position on different dates of service, within 365 days of each other, and in the same continuous enrollment period during the patient identification period. The ***fibrosing ILD diagnosis date*** will be defined as the date of the first fibrosing ILD diagnosis. The two fibrosing ILD diagnosis codes can be one of the following combinations:
 - 2 fibrosis codes
 - 1 fibrosis code & 1 ILD code that requires fibrosis code
- ≥ 18 years of age as of the fibrosing ILD diagnosis date
- Continuous enrollment with medical and pharmacy coverage for 12 months prior to the fibrosing ILD diagnosis date (***pre-ILD baseline period***)

Exclusion Criteria

- Fibrosing ILD diagnosis in the 12-month pre-ILD baseline period
- Unknown gender or geographic region

Cohort Assignment

Patients meeting initial selection criteria for Aim 1 will be assigned to cohorts based on known cause of fibrosis:

- **IPF**— ≥ 2 medical claims with diagnosis for IPF in any position during the study period
- **Non-IPF ILD**— < 2 medical claims with diagnosis for IPF during the study period

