7.3.3 Aim 2 Outcomes

7.3.3.1 Primary Outcomes

All primary outcomes will be measured in the Aim 2 and Further Aim follow-up period, unless specified otherwise.

- **Time to disease progression**—Pulmonary function test (PFT) results will be captured as available in the database in the pre-ILD baseline, pre-index baseline, and Aim 2 follow-up periods among the subset of patients who have EHR data during the same

time of ILD diagnosis and oxygen therapy. All valid result values will be captured. Values closest to the fibrosing ILD diagnosis date will be reported for the pre-ILD baseline period; values closest to the index date will be reported for the pre-index baseline period; the latest values prior to the end of follow-up will be reported for the Aim 2 follow-up period. PFT tests may potentially include forced expiratory volume in 1 second (FEV₁), forced vital capacity (FVC), FEV₁/FVC ratio, lung volumes, and diffusing capacity for carbon monoxide (DLCO), as available.

Among patients or matched pairs with FVC results in the pre-index and follow-up periods, disease progression will be defined as a 10% relative change between the pre-index value and the follow-up value. Time to disease progression will be reported. Additionally, time in days from pre-index FVC result to the index date and from index date to follow-up FVC result will be reported.

- **Time to all-cause mortality**—We will assign the date of death as the 15th day in the month of death. Time to all-cause mortality will be calculated as time between index date and mortality date.

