7.3.5.2 Clinical Characteristics

- **Underlying ILD type**—Patients will be classified into the following underlying ILD types based on claims from the entire study period: autoimmune ILD, HP, sarcoidosis, unclassified ILD/IIP, and multiple. The underlying ILD type will be defined based on the presence of ≥ 1 specific ICD-10-CM diagnosis code for autoimmune ILD, HP, and sarcoidosis. Patients without any underlying ILD diagnosis will be classified into the unclassified ILD/IIP type. Patients with diagnoses for >1 underlying ILD types will be classified as multiple.
- **Respiratory diseases**—Separate indicator variables will be created for the presence of ≥ 1 diagnosis code in any position on a medical claim. The following conditions will be included: pulmonary hypertension, acute respiratory failure, asthma, COPD, pneumonia, lung transplantation, upper respiratory tract infection, lower respiratory tract infection, lung cancer, and cystic fibrosis.
- **Other clinical characteristics** – Similar to respiratory disease, a separate indicator variables will be created for the presence of ≥ 1 diagnosis code in any position on a medical claim. The following conditions will be included: gastroesophageal reflux disease (GERD), heart failure, and obstructive sleep apnea.
- **Quan-Charlson comorbidity score**—A comorbidity score will be calculated based on the presence of diagnosis codes on medical claims.^{10, 11} The Quan-Charlson comorbidity score will also be categorized into the following groups: zero, one to two, three to four, and five or more.
- **Comorbid conditions**—General comorbid conditions will be defined using the Clinical Classifications Software managed by the Agency for Healthcare Research and Quality (AHRQ).¹² This measure generates indicator variables for specific disease

conditions based on ICD-9-CM and ICD-10-CM diagnoses. The top 20 comorbid conditions will be presented.

[figure not shown]
- **Smoking**—An indicator variable will be created to identify patients with evidence of current or prior tobacco use based on diagnosis codes or pharmacy fills for smoking cessation treatments (bupropion, varenicline tartrate, or nicotine [inhalation, gum, lozenge, transdermal]).
- **Pulmonary rehabilitation**—Indicator and count variables will be created for the presence of procedure codes for pulmonary rehabilitation.

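### Lung transplantation neither excludes patients nor ends follow-up in the visible rules, so post-transplant FVC and survival can be counted as outcomes of fibrotic ILD

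*Combined protocol and SAP*

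**What the plan says.** Section 5 places transplantation among the treatments for this disease: "Other commonly prescribed treatment options are corticosteroids, immunosuppressants, opioids, and lung transplantation". In the visible methods it appears once more, in Section 7.3.5.2, within a list of respiratory-disease indicators: "pulmonary hypertension, acute respiratory failure, asthma, COPD, pneumonia, lung transplantation". Section 7.3.5 and Table 1 place those indicators in the pre-ILD and pre-index baseline periods, not in follow-up.

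The exclusions in Section 7.2.2 are "Fibrosing ILD diagnosis in the 12-month pre-ILD baseline period" and "Unknown gender or geographic region"; the abstract adds unknown insurance type. None concerns transplantation.

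Aim 1 follow-up runs from the fibrosing ILD diagnosis date, "continuing until the earliest of the following: disenrollment from the health plan, death, or end of the study period". Aim 2 follow-up runs from the index date "until the earliest of the following: disenrollment from the health plan, death, or the end of the study period". Section 7.3 adds for Aim 2: "Matched pairs will be given the same duration of follow-up". The Kaplan-Meier censoring rule in Section 7.6.1.2 repeats the three events, makes competing-event methods optional, and gives death as the only example.

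For pulmonary function, Section 7.3.3.1 states that "the latest values prior to the end of follow-up will be reported for the Aim 2 follow-up period". Progression is a 10% relative change in FVC from the pre-index value, with no direction given. Mortality is timed from index to death.

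**The concern.** A transplant replaces the organ whose decline the study sets out to measure. Under the stated rules, a patient transplanted during follow-up keeps contributing time and outcomes, and the latest-value rule prefers a post-transplant FVC wherever one exists. That value is then scored as progression or non-progression of fibrotic ILD, although it describes a different lung. Hypoxemia and exacerbations recorded after transplant have the same problem. For mortality, survival obtained through transplant is attributed to oxygen or to no oxygen.

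If transplantation is more frequent in one cohort, the comparison is biased. Greater frequency in the oxygen cohort is clinically plausible, but the documents give no figure for it. Matching on a baseline indicator cannot deal with a transplant that happens after the index date.

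In Aim 1, a patient transplanted without earlier oxygen use stays at risk of initiating oxygen. Because one oxygen code is enough (Section 7.3.1.1), that patient may also be counted as an initiator from peri-operative oxygen.

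**Working it through.** **Text check.** Each visible rule that could deal with transplantation:

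- Eligibility (abstract, 7.2.2, 7.2.3): not mentioned.
- End of follow-up, Aims 1 and 2 (7.1, figure notes, 7.3): disenrollment, death, end of study only.
- Aim 1 censoring and competing events (7.6.1.2): the same three events; death is the only example of a competing event.
- Outcomes (7.3.3): latest FVC before the end of follow-up; mortality from index to death; no stop at transplant.
- Covariates (7.3.5.2): baseline indicator only.
- Limitations (7.8): not mentioned.

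There is no planned figure to reproduce. All rates below are assumptions for illustration.

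**Mortality.** Assume true mortality m = 30% in both cohorts, no oxygen effect, transplant shares tO (oxygen) and tC (comparator), and a fraction a of transplants averting one death within follow-up:

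RR = (m − a·tO) / (m − a·tC)

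- 1% vs 1%, a = 1: 0.29/0.29 = 1.00
- 4% vs 1%, a = 1: 0.26/0.29 = 0.90
- 4% vs 0%, a = 1: 0.26/0.30 = 0.87
- 4% vs 1%, a = 0.5: 0.28/0.295 = 0.95

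**FVC progression.** Assume true progression p is the same in both cohorts. The two readings of the 10% rule are:

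- Any change counts and every post-transplant value meets it: observed p = p(1 − t) + t.
- Only decline counts and no post-transplant value meets it: observed p = p(1 − t).

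Worked case, p = 20%, t = 3% vs 0.5%. Any change: (0.20 × 0.97 + 0.03)/(0.20 × 0.995 + 0.005) = 0.224/0.204 = 1.10. Decline only: 0.194/0.199 = 0.975.

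| Transplanted, oxygen vs comparator | Any change, p = 20% | Any change, p = 40% | Decline only, either p |
|---|---|---|---|
| 1% vs 0.2% | 1.03 | 1.01 | 0.99 |
| 3% vs 0.5% | 1.10 | 1.04 | 0.975 |
| 5% vs 1% | 1.15 | 1.06 | 0.96 |

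The sign of the bias depends on the direction of change, which the protocol does not state.

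**Aim 1.** Time to initiation is analysed only in patients without baseline oxygen. A patient who starts oxygen and is transplanted later has already had the event. Only those transplanted with no earlier oxygen are affected.

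**The case against.** - **The Aim 2 analysis section cannot be seen.** Section 7.2.3 refers to Section 7.6.2.2, but the available text passes from 7.6.1.3 to 7.7. A model, competing-event method or sensitivity analysis for transplant may be there. Section 7.2.3 also lets the team revise the Aim 2 criteria after Aim 1. This stands, and it limits the claim to the visible rules. Those rules nevertheless include the follow-up definitions, the latest-FVC rule and the Aim 1 censoring rule.
- **Earlier transplants are partly dealt with.** A fibrosing ILD diagnosis in the 12 months before the diagnosis date excludes the patient, which should remove many transplanted for this disease in that window, and both baselines record the indicator. That helps at Aim 1 entry. It does nothing for a transplant between diagnosis and index, or during follow-up.
- **Following all-cause mortality through later treatment is a legitimate choice.** Agreed; it should be kept. The same argument does not cover FVC, where the measured organ has changed.
- **Stronger readings.** A reader might infer that the omission flatters oxygen on every outcome. The undirected 10% change means the FVC bias could run against oxygen. A reader might also infer that Aim 1 times to oxygen are broadly misstated, but patients already on oxygen before transplant are unaffected. Lastly, a reader might take the transplanted share of the oxygen cohort divided by its mortality as the size of the bias. That ignores transplants among comparators and assumes that every transplant averts a death.

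**Conclusion.** The point holds for the visible rules. Followed as written, they allow a donor-lung FVC to be scored as the course of fibrotic ILD, and they credit post-transplant survival to the exposure cohort. That is a measurement error for lung-based outcomes rather than a mere lack of detail, and it should be corrected.

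The size cannot be established from the documents. Under the assumptions shown, the spurious mortality risk ratio lies between 1.0 and 0.87, and nearer 1 if fewer deaths are averted. The FVC ratio lies between 0.96 and 1.15, depending on the reading of the 10% rule. These ranges rest on assumed transplant shares, 30% mortality and 20–40% progression. Any bias against or in favour of oxygen also requires unequal transplant rates, which only counts by cohort can show. The Aim 1 effect is limited to patients transplanted without earlier oxygen.

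**What to change.** - Build a dated transplant flag from procedure and diagnosis codes across baseline and follow-up. The planned diagnosis-code indicator need not date the operation.
- Exclude patients with a transplant on or before the fibrosing ILD diagnosis date (Aim 1) or the index date (Aim 2). The Aim 2 exclusion also removes patients whose first oxygen claim is on or after the transplant date.
- In Aim 2, use only pre-transplant FVC, hypoxemia and exacerbation data. Treat transplant as a competing event, or as censoring with a sensitivity analysis.
- Keep all-cause mortality and report death-or-transplant beside it.
- In Aim 1, treat transplant as a competing event for oxygen initiation.
- Report transplant counts by cohort, and state the direction of the 10% FVC change.
- If Section 7.6.2 already contains such rules, bring Section 7.3 into line with them. Settle the rule before Aim 2 outcomes are seen.

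The cost is one additional dated variable, a few sentences, and a small loss of patients and person-time. There are two further costs. Censoring at transplant may be informative, which is why the competing-event and composite analyses are needed. Under the equal-follow-up rule for pairs, stopping one member may also truncate the matched partner, so the protocol should say whether it does.

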6. RESEARCH QUESTION AND OBJECTIVES

The purpose of this study is to examine oxygen therapy utilization and assess its impact on clinical and economic outcomes of ILD patients. There are three aims for this project:

Aim 1: *To describe initiation and use of oxygen therapy among patients with fibrotic ILD. The specific objectives for Aim 1 are to:*

- Examine the incidence and prevalence of oxygen therapy among patients with fibrotic ILD
- Assess the time to first oxygen therapy among fibrotic ILD patients naïve to oxygen therapy, and examine factors/variables associated with oxygen therapy initiation

Aim 2: *To assess the impact of oxygen therapy on clinical outcomes among patients with fibrotic ILD. The specific objective for Aim 2 is to:*

- Evaluate the impact of oxygen therapy initiation on clinical outcomes, including disease progression and mortality, among fibrotic ILD patients

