7. RESEARCH METHODS

7.1 STUDY DESIGN

[figure not shown]
This is a non-interventional study of patients enrolled in a commercial, Medicaid, or Medicare plan, using existing administrative claims and EHR data in Optum's Market Clarity Integrated Claims + Clinical database for the period of 01 October 2015 through 30 June 2022 (study period). The study period may be extended through latest data available at the time of study implementation to increase study sample.

To describe the initiation and use of oxygen therapy after first fibrosing ILD diagnosis (**Aim 1**), patients aged ≥ 18 years with newly diagnosed fibrosing ILD will be identified from 01 October 2016 through 30 June 2022 (patient identification period). A schematic of the observation and identification periods is presented in Figure 1. Patients will be required to have 12 months of baseline continuous enrollment prior to fibrosing ILD diagnosis for collecting patient demographics and clinical characteristics. The pre-ILD baseline period will also be used to describe baseline prevalence of oxygen therapy use. Patients will be followed for a variable period from the fibrosing ILD diagnosis date (Section 7.2.2) until the earlier of disenrollment from the health plan, end of study period, or death. Oxygen therapy use will be described, and results will be stratified by underlying cause of fibrosis (e.g., IPF vs non-IPF ILD). Factors associated with initiation of oxygen therapy will be assessed using multivariable methods.

To assess the impact of oxygen therapy use on outcomes (**Aim 2 and Further Aim**), patients with fibrosing ILD who initiated oxygen therapy will be propensity score matched to those who did not yet initiate oxygen therapy. A schematic of the observation and identification periods is presented in Figure 2. The index date will be defined as the date of oxygen therapy initiation for oxygen therapy cohort, or a date that is eligible for index and is similar to the

[figure not shown]
matched case's index date for no oxygen therapy cohort. Disease progression, acute exacerbations, health care resource utilization (HCRU), and health care costs in the Aim 2 follow-up period will be described and compared between matched cohorts. Outcomes will be modelled using multivariable methods.

Figure 1. Observation and Identification Periods: Aim 1

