7.2.3 Study population: Aim 2 [REDACTED]

The analysis for Aim 2 and Further Aim will include patients identified for Aim 1 in Section 7.2.2 who meet the following additional selection criteria. Final oxygen therapy cohorts will be determined during the propensity score matching (PSM) procedure outlined in Section 7.6.2.2.

- **Oxygen therapy cohort**

- ILD patients with ≥ 1 medical claim for oxygen therapy after fibrosing ILD diagnosis. The ***index date*** will be defined as the first date of a claim for oxygen therapy.

- **No oxygen therapy cohort**
 - Matched to a patient in the oxygen therapy cohort. The **index date** will be assigned as a date that is eligible to set an index date (i.e., similar to the matched oxygen therapy patient in time from the fibrosing ILD diagnosis date to the index date, and during the same continuous enrollment period as the fibrosing ILD diagnosis date).

NOTE: Following review of results from Aim 1, the study team will determine whether criteria for Aim 2 and Further Aim require revision.

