7.3.2 Aim 2 Exposures

The exposure of interest is oxygen therapy versus no oxygen therapy among patients with fibrosing ILD and is defined based on evidence of oxygen therapy following ILD diagnosis, as described in Section 7.2.3.

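### Aim 2 targets oxygen initiation, but its visible index and exposure rules disagree with one another and carry no oxygen-naive restriction

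*Combined protocol and SAP*

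**What the plan says.** The aim is about initiation. Section 6 states the Aim 2 objective as: "Evaluate the impact of oxygen therapy initiation on clinical outcomes, including disease progression and mortality, among fibrotic ILD patients". Section 7.1 follows suit: "The index date will be defined as the date of oxygen therapy initiation for oxygen therapy cohort", and these patients "will be propensity score matched to those who did not yet initiate oxygen therapy".

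The operational rules are worded differently:

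- **Eligibility (Section 7.2.3).** The oxygen cohort needs at least one "medical claim for oxygen therapy after fibrosing ILD diagnosis".
- **Index date (Section 7.3).** It is "the first date following the fibrosing ILD diagnosis date with a claim with diagnosis for oxygen therapy".
- **Exposure (Section 7.3.2).** It "is defined based on evidence of oxygen therapy following ILD diagnosis".
- **Index date elsewhere.** The abstract, Section 7.2.3 and the second Figure 2 note give the first date of an oxygen claim, with no starting point for what counts as first. The first Figure 2 note places the ILD diagnosis before the index date.

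Section 7.2.3 also sends the reader onward: "Final oxygen therapy cohorts will be determined during the propensity score matching (PSM) procedure outlined in Section 7.6.2.2". That section is not in the public text.

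**The concern.** A comparison of starters with patients who have not yet started needs a rule that establishes that the starters are new. The plan has such a rule for Aim 1: Sections 7.3.1.1 and 7.6.1.2 limit time to initiation to patients with no oxygen evidence in the pre-ILD baseline. No visible Aim 2 criterion repeats it.

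The oxygen cohort could then mix true starters with patients who had oxygen before diagnosis and whose index date is merely their next claim. For the latter, follow-up for mortality and progression would begin after treatment began. The bias could go either way. Earlier users may have survived an early high-risk period, or they may have more advanced disease. A large sample does not cure this.

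Section 7.8 warns that prevalent ILD may be taken for new ILD. It gives no matching warning for prevalent oxygen use.

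**Working it through.** The plan states no figure to reproduce here, so the check is to set the rules side by side and apply them.

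1. **Source population.** Section 7.2.3 draws Aim 2 from the Aim 1 patients. The Section 7.2.2 exclusions are "Fibrosing ILD diagnosis in the 12-month pre-ILD baseline period" and unknown demographic fields. Earlier oxygen is not among them. Section 7.1 plans to describe oxygen prevalence in the pre-ILD baseline of this same population, so earlier users are expected in it.

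2. **Where the naive limit sits.** In Sections 7.3.1.1 and 7.6.1.2 it belongs to one outcome definition and one analysis. It is not a Section 7.2.2 criterion, so Aim 2 does not inherit it.

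3. **Section 7.3 applied literally.** Let diagnosis be day 0. Take a patient with oxygen evidence on day −a (a from 1 to 365) whose first later claim is on day +d (d at least 1). The index is day +d. Oxygen began on day −a or earlier, so follow-up starts at least d − (−a) = a + d days after initiation. For a patient whose first oxygen is on day +d, that gap is 0. Both enter the same cohort.

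4. **The unqualified wording applied instead.** If first means first ever, the same patient's index would be day −a or earlier. The Figure 2 note requires diagnosis to come before index, so the patient has no valid index date. The Section 7.2.3 eligibility line still admits the patient. The two readings therefore give different cohorts, and neither states an exclusion.

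5. **Controls.** A patient with oxygen before diagnosis and none afterwards is not expressly barred from the no-oxygen cohort, although Section 7.1 describes controls as not yet having initiated.

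6. **Oxygen billed on the diagnosis date.** Aim 1 follow-up starts on that date, so for Aim 1 the patient initiates on day 0. Section 7.3 counts only later dates for Aim 2, so the same patient receives a later index.

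7. **Size.** Baseline oxygen prevalence is not given. None of the five Table 3 counts (1,179,017; 214,725; 212,466; 80,151; 34,299) removes earlier oxygen users, so the share cannot be recovered. For the cost of a restriction only, and purely as an assumption, suppose 10%, 30% or 50% of the 34,299 had earlier oxygen:
   - 34,299 × 0.90 ≈ 30,869
   - 34,299 × 0.70 ≈ 24,009
   - 34,299 × 0.50 ≈ 17,150

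   Table 3 uses looser criteria than the study (one diagnosis, 6 months of enrollment), so these are not forecasts of the Aim 2 cohort.

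**The case against.** The strongest objection is that the deciding text is withheld. Section 7.2.3 says the cohorts are finalised in Section 7.6.2.2, and a look-back or a match on earlier oxygen could be there. This stands, and it limits the point to the visible definitions. A reader might infer that the plan has no oxygen-free look-back at all, or that the oxygen cohort will contain prevalent users. The documents do not support either inference.

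Second, the wording is not uniformly permissive. The abstract, Section 7.2.3 and Figure 2 can be read as first ever, Section 7.1 speaks of initiation, and Section 7.3.1.1 glosses the index date as the oxygen initiation date. This also stands as evidence of intent. It makes the fault an inconsistency rather than a consistent rule admitting earlier users. It does not supply an exclusion, and Section 7.3 is the most specific index definition.

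Third, a reader might infer that the matching covariates are measured on treatment because the pre-index window overlaps oxygen use. No visible text says that this window feeds the matching. Section 7.8 speaks of similarity on pre-ILD characteristics, and Section 7.3.5 lists both windows. That inference is not made here.

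Fourth, Section 7.3.1.1 accepts a single code as oxygen evidence, so earlier evidence need not mean continuing use. That is correct, and it is a real cost of a strict look-back.

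Finally, the note in Section 7.2.3 allows the Aim 2 criteria to be revised after Aim 1. It names no oxygen rule, so it does not settle the matter.

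**Conclusion.** The point holds as an inconsistency within the visible Aim 2 definitions, and between them and the stated aim. Under Section 7.3 as written, a patient with oxygen evidence before diagnosis and a claim afterwards is indexed as an initiator, with follow-up starting late. The visible text gives no figure for how many such patients there are, and neither the size nor the direction of the bias can be computed. The conclusion assumes that Section 7.6.2.2 does not already impose the restriction. If it does, what remains is to align the wording and add a cross-reference. The matter is worth correcting because it affects who counts as exposed, and from when, in the mortality and progression comparisons.

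**What to change.** First check Section 7.6.2.2. If it already restricts Aim 2 to oxygen-naive patients, cross-reference it from Sections 7.2.3 and 7.3. If not:

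- Require for both cohorts no oxygen evidence, by the Section 7.3.1.1 codes, in the 12-month pre-ILD baseline. For controls, require none up to the assigned index date.
- Define the oxygen cohort's index date as the first oxygen evidence in these oxygen-naive patients. Bring the abstract, the Figure 2 notes and Sections 7.2.3, 7.3 and 7.3.2 to that one wording.
- State one explicit rule for oxygen first billed on the diagnosis date: either index on that day and amend the Figure 2 note, or exclude.
- Report the number of patients removed.

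The work is one eligibility criterion and aligned definitions, using codes that Aim 1 already captures. The cost is a smaller oxygen cohort, by an amount the documents do not allow to be estimated, including the loss of patients with a single isolated earlier oxygen code.
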